9. SAFETY ANALYSIS

Safety and tolerability of tipifarnib will be assessed based on the following:

- Incidence, duration and severity of treatment-emergent adverse events, serious adverse events, adverse events resulting in permanent discontinuation of study drug, and deaths within approximately 30 days from the last dose of study drug (or immediately before the administration of another anti-cancer treatment)
- Laboratory test results
 - Serum Chemistry: Blood Urea Nitrogen (or Uric Acid), Creatinine, Sodium, Potassium, Calcium, Total Protein, Albumin, Total Bilirubin, Alkaline Phosphatase, ALT/SGOT, AST/SGPT, Lactate Dehydrogenase;
 - Hematology: White Blood Cell Count, Hemoglobin, Platelet Count, Neutrophils, Lymphocytes, Monocytes;
 - Coagulation Panel: Prothrombin Time and International Normalized Ratio (PT/INR), Activated Partial Thromboplastin Time (APTT);
- Changes in vital signs including blood pressure, pulse, and temperature;
- Changes in electrocardiogram results.

Adverse events will be coded using MedDRA per the Data Coding Plan. Treatment-emergent adverse events are defined as adverse events that start on or after the first dose of study drug and within 30 days of the last administration of study drug or immediately before the initiation of any other anticancer therapy. Adverse events will be summarized by the number and percentage of subjects who experienced the event, according to system organ class and preferred term. A subject reporting multiple cases of the same adverse event will be counted once within each system organ class and similarly counted once within each preferred term.

Unless specified otherwise, the denominator for these calculations will be based on the number of subjects who received at least one administration of tipifarnib regardless of the total number of doses or treatment cycles administered. These conventions will be appropriately modified to calculate AE incidence rates separately for each cycle that study therapy is administered. AE incidence rates may also be calculated based on other measures of subject exposure (e.g., total number of treatment cycles administered).

AE durations will be calculated using all TEAEs. For AEs that are still ongoing at the end of study, we will use the last contact date as the end of AE stop date for calculating the duration of AEs. Median, minimum and maximum of AE durations will be reported.

AEs will also be summarized by National Cancer Institute – Common Terminology Criteria for Adverse Events (NCI-CTCAE) version 4.03 severity grade and by relationship to each study drug. Additional summaries may also be provided for SAEs, and events resulting in the permanent discontinuation of therapy. All AEs will be included in individual subject listings.

The incidence of all Grade 3 and 4 hematological NCI-CTCAE severity grades will be provided by treatment cycle and across all treatment cycles. The severity grades for laboratory tests will be based on NCI-CTCAE version 4.03 criteria. The use of blood transfusions (platelets, red blood cells) and/or growth factor support will be reported. Similar analyses will be done for chemistry tests.

Hematologic abnormalities reported as AEs that were coded to preferred terms in the Investigations SOC will be mapped to appropriate terms in the Blood and Lymphatic System SOC for tabulation for the following categories:

- Platelet count decreased = Thrombocytopenia;
- Neutrophil count decreased = Neutropenia;
- White blood cell count decreased = Leukopenia;
- Lymphocyte count decreased = Lymphopenia.

Vital sign results (blood pressure, pulse, respirations, and temperature) will be summarized descriptively for each scheduled and unscheduled protocol time point. Changes will be calculated relative to the assessments at baseline and on the first day of each cycle of therapy.

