6.2 Secondary Objectives and Endpoints

Secondary Objective 1: To determine the antitumor activity in terms of PFS and DOR of tipifarnib in subjects with relapsed or refractory PTCL.

Secondary Endpoint 1: PFS and DOR according to the Lugano Classification and/or mSWAT.

Secondary Objective 2: Safety and tolerability of tipifarnib in subjects with relapsed or refractory PTCL.

Secondary Endpoint 2: Treatment-emergent adverse events (TEAE) and SAEs evaluated according to NCI CTCAE v.4.03.

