7 SUBJECT SELECTION

7.1 Inclusion Criteria

For inclusion of a subject in the study, all of the following inclusion criteria must be fulfilled:

1. Subject is at least 18 years of age.
2. Subject has a diagnosis of PTCL according to the most recent edition of the World Health Organization (WHO) Classification of Tumors of Hematopoietic or Lymphoid Tissues as follows:
 - a. ALCL, ALK positive
 - b. ALCL, ALK negative
 - c. AITL

- d. Enteropathy-associated T-cell lymphoma
- e. Extranodal natural killer (NK) T-cell lymphoma, nasal type
- f. Hepatosplenic T-cell lymphoma
- g. PTCL, NOS
- h. Subcutaneous panniculitis-like T-cell lymphoma

For enrollment into the AITL expansion cohort, subjects must have the diagnosis of AITL, nodal PTCL with T-follicular helper phenotype or follicular PTCL.

For enrollment into the CXCL12+ PTCL expansion cohort, subjects must have the diagnosis of PTCL (a – h subtypes listed above, except AITL), consent to provide buccal swabs for CXCL12 SNP testing, and be found to be CXCL12+ based on testing by a Sponsor approved methodology. Once (if) the AITL cohort has completed accrual, subjects with AITL histology and CXCL12+ status may be enrolled in the CXCL12+ PTCL expansion cohort.

- 3. Subject has relapsed or are refractory to at least 1 prior systemic cytotoxic therapy. Subjects must have received conventional therapy as a prior therapy.
- 4. Subject has consented to provide at least 6 unstained tumor slides (10 preferred) or an FFPE block for biomarker testing. Tumor tissue may be obtained from prior archival diagnostic biopsies. If the site is unable to confirm during screening that sufficient archival biopsy is available, the subject must consent to a pretreatment biopsy for inclusion in this study.
- 5. Subject has measurable disease according to the Lugano Classification and/or mSWAT.
- 6. At least 2 weeks since the last systemic therapy regimen prior to enrollment. Subjects must have recovered to NCI CTCAE v. 4.03 < Grade 2 from all acute toxicities (excluding Grade 2 toxicities that are not considered a safety risk by the Sponsor and Investigator) or toxicity must be deemed irreversible by the Investigator.
- 7. At least 2 weeks since last radiotherapy if radiation was localized to the only site of measurable disease, unless there is documentation of disease progression of the irradiated site. Subjects must have recovered from all acute toxicities from radiotherapy.
- 8. ECOG performance status of 0-2 ([Appendix 1](#)).

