10.7 Events Not to Be Considered as AEs/SAEs

Medical conditions are present at the initial trial visit that do not worsen in severity or frequency during the trial are defined as Baseline Medical Conditions, and are NOT to be considered AEs. Progression of underlying disease is not an AE and therefore not an SAE per se, rather an efficacy end-point, unless deemed to be causally related to administration of IPs. However, if adverse signs or symptoms occur in association with disease progression then these should be recorded as AEs and reported as SAEs if meeting any seriousness criteria.

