10.9 Adverse Event Reporting Period

The adverse event reporting period for safety surveillance begins when the subject is included into the trial (date of first signature of informed consent) and continues through the trial’s post-treatment follow-up period, defined as 30 days from the final administration of the trial treatment or immediately before initiation of any other anticancer therapy, whichever comes first.

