12.2.2 Safety and Tolerability

Safety and tolerability of tipifarnib will be assessed based on the following:

[figure not shown]
- Incidence, duration, and severity of treatment-emergent adverse events, serious adverse events, adverse events resulting in permanent discontinuation of study drug, and deaths within approximately 30 days from the last dose of study drug (or immediately before the administration of another anti-cancer treatment)
- Changes in vital signs including blood pressure, pulse, and temperature
- Changes in electrocardiogram results

Adverse events will be coded using the latest available version of the Medical Dictionary for Regulatory Activities (MedDRA). Treatment-emergent adverse events are defined as adverse events that start on or after the first dose of study drug and within approximately 30 days of the last administration of study drug. Adverse events will be summarized by the number and percentage of subjects who experienced the event, according to system organ class and preferred term. A subject reporting multiple cases of the same adverse event will be counted once within each system organ class and similarly counted once within each preferred term.

Unless specified otherwise, the denominator for these calculations will be based on the number of subjects who received at least one administration of tipifarnib, irrespective of the total number of doses or treatment cycles administered. These conventions will be appropriately modified to calculate AE incidence rates separately for each cycle that study therapy is administered. AE incidence rates may also be calculated based on other measures of subject exposure (e.g., total number of treatment cycles administered). AEs will also be summarized by NCI-CTCAE version 4.03 severity grade and by relationship to each study drug. Additional summaries may also be provided for SAEs, and events resulting in the permanent discontinuation of therapy. All AEs will be included in individual subject listings.

The incidence of grade 3 and 4 hematological toxicities (including neutropenia, thrombocytopenia, and anemia) will be provided by treatment cycle and across all treatment cycles. The toxicity grades for laboratory tests will be based on NCI-CTCAE version 4.03 criteria. The use of blood transfusions (platelets, red blood cells) and/or growth factor support will be reported. Similar analyses will be done for selected chemistry tests (including liver and renal function tests).

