14. CHANGES IN THE STATISTICAL METHODS FROM THOSE STATED IN THE PROTOCOL

For the efficacy analysis, the estimation of the objective response rate will be estimated for all subjects in the indicated study population and will not be done separately for each tumor histology type evaluated.

An exploratory Efficacy Analysis (to be performed if results warrant) has been added and is described in Section [8.3](#) of this document.

Summaries for hematology and chemistry-related AEs have been added to the safety analysis.

Laboratory change and shift from baseline will not be performed.

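### The TEAE definition has no worsening clause, so an adverse event that begins before the first dose and worsens on tipifarnib can be left out of the TEAE tables

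*SAP*

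**What the plan says.** Secondary endpoint 2 in Protocol 6.2 is "Treatment-emergent adverse events (TEAE) and SAEs evaluated according to NCI CTCAE v.4.03". Both documents define a TEAE by when the event starts. Protocol 12.2.2 reads "Treatment-emergent adverse events are defined as adverse events that start on or after the first dose of study drug and within approximately 30 days", counted from the final dose. SAP 9 has the same lower limit, "Treatment-emergent adverse events are defined as adverse events that start on or after the first dose of study drug", and sets the upper limit at "within 30 days of the last administration of study drug or immediately before the initiation of any other anticancer therapy". Neither mentions an event or condition that is already present at first dose and then worsens.

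Four other provisions bear on this:

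- **Collection period.** Under Protocol 10.9, AE reporting "begins when the subject is included into the trial (date of first signature of informed consent"), which precedes dosing. Protocol 11.1 lists AE assessment among the screening procedures.
- **Entry conditions.** Inclusion criterion 6 in Protocol 7.1 requires recovery from acute toxicities to below Grade 2, "excluding Grade 2 toxicities that are not considered a safety risk by the Sponsor and Investigator". It also accepts toxicity that the investigator deems irreversible.
- **Baseline conditions.** Protocol 10.7 says that conditions present at the initial visit "that do not worsen in severity or frequency during the trial are defined as Baseline Medical Conditions" and are not AEs. By implication, one that does worsen is an AE.
- **Recording.** Protocol 10.8 has unfavorable changes recorded as AEs with onset and resolution dates. It leaves further detail to eCRF conventions that are separate from these documents.

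**The concern.** The rule that makes something an AE and the rule that makes it treatment-emergent do not match. Protocol 10.7 turns on worsening; the TEAE definition turns on start date alone. An event can therefore be an AE because of what happened on tipifarnib and still not count as a TEAE, because its recorded start is before the first dose.

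Most SAP 9.1 tables are built on TEAEs: overall incidence, exposure-adjusted rate, maximum CTCAE grade, duration, drug-related events, Grade 3 or higher drug-related events, and events leading to permanent discontinuation. For worsening events the error goes one way, toward too few. The trial has no control arm against which a shared undercount would balance out. The last extension, of up to 20 subjects with AITL and related histologies, was added expressly to characterize safety and tolerability (Protocol 8.1 and 12.4, SAP 3.1).

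**Working it through.** No sample size, error rate or event count is involved, so the check is to apply the definition to each way in which a worsening event can be recorded.

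**Step 1. Can an AE start before first dose?** Yes. Collection begins at consent, and screening runs up to 28 days before Cycle 1 Day 1. Protocol 11.1 also lets the buccal swab be taken earlier than that.

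**Step 2. Can a subject enter with an existing toxicity?** Yes, under criterion 6, within the liver, renal and hematologic limits of criteria 9 to 11. Exclusion 7 bars non-tolerable neuropathy of Grade 2 or above, so tolerable Grade 2 neuropathy is not barred by that criterion.

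**Step 3. Apply the start-date rule.**

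| Event | How it is recorded | Start date used | TEAE? |
|---|---|---|---|
| AE begins after consent, before dosing; grade rises on drug | One record | Before first dose | No |
| Same | New record at worsening | After first dose | Yes |
| Condition present at initial visit; worsens on drug | AE dated at worsening | After first dose | Yes |
| Same | AE dated at original onset | Before first dose | No |

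The first row follows from the definition as written. The last two rows depend on an onset-date rule that neither document states.

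A hypothetical case for the first row: Grade 1 rash begins during screening, becomes Grade 3 in Cycle 2 without being serious, and stays one record. It is an AE and appears in the listings. It is absent from the TEAE incidence, maximum-grade, drug-related and duration tables, and SAP 9.1 has no separate rash table.

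**Step 4. Which outputs would still show the event?** These are not tied to the TEAE start date by their description:

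- SAE tables by SOC and PT (SAP 9.1);
- Grade 3 or 4 fatigue and Grade 3 or 4 gastrointestinal tables (SAP 9.1);
- Grade 3 or higher hematology and chemistry incidence by cycle, and transfusion or growth factor use (SAP 9.2);
- listings of all AEs (SAP 9).

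What remains exposed is mainly the non-serious, non-laboratory event outside those two Grade 3 or 4 tables. Tolerable neuropathy that worsens is an example of the entry-condition route.

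**Step 5. Size.** For one AE term, the undercount as a share of subjects is p × w × k. Here p is the share with the event or condition before dosing, w the share of those who worsen on drug, and k the share of those worsenings kept under the original start date. The documents give none of the three. For entry conditions, k = 0 if every worsening is re-dated, and the undercount is then 0.

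**The case against.** The strongest reply rests on Protocol 10.7 and 10.8. A residual toxicity present at the initial visit is not an AE until it worsens, so the natural onset of the AE is the date of worsening. That date is after first dose, and the event is a TEAE. Record-splitting and dating may also be settled in the eCRF conventions. For conditions present at entry this reply largely stands: a reader might infer from criterion 6 that subjects admitted with ongoing toxicity necessarily drop out of the TEAE counts, and the documents do not show that. They show only that the onset date is unstated.

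The reply does not reach an AE that is already open between consent and first dose. Such an event is an AE from its start. Nothing in either document requires a second record when its grade rises.

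Two further inferences should be resisted:

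- SAP 14 says "Laboratory change and shift from baseline will not be performed", which might suggest that no planned table compares treatment with the pre-treatment state. That is not so: SAP 9.3 tabulates vital-sign change from baseline, and SAP 9.4 tabulates ECG category shift from screening. What is missing is such a comparison for laboratory values and symptomatic AEs.
- Fatigue rising from Grade 2 to Grade 3 looks like a ready example of a lost event, but it falls within the scope of the separate Grade 3 or 4 fatigue table, which is not labelled as TEAE-only.

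**Conclusion.** The gap is real but limited. It is certain for an AE that starts between consent and first dose, worsens on tipifarnib and is kept as one record. It is possible, depending on an unstated dating rule, for a condition present at entry. It affects the TEAE component of secondary endpoint 2, not the SAE component, and falls mainly on non-serious, non-laboratory events. It has no bearing on ORR, the sample size or any test.

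The documents do not support a numerical size. A reader might assume that 20% of subjects enter with a condition and that 25% to 50% of those worsen. That gives 0.20 × 0.25 = 5% to 0.20 × 0.50 = 10%, or 3.5 to 7 of 70 subjects for that term. Both inputs are assumptions, and the result also sets k = 1, meaning that every worsening keeps its original date. With k between 0 and 1, the same inputs give anything from 0 to 7.

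The change should still be made. Without it, identical clinical courses can be counted or not according to how a site enters them, and the correction is cheap.

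**What to change.** In Protocol 12.2.2 and SAP 9, define a TEAE as an AE that starts, or a pre-existing condition or AE that worsens in severity or frequency, on or after the first dose and within the existing end window. This brings the definition into line with Protocol 10.7. Add that, for a worsened event, onset for this purpose is the date of worsening and the worsened grade is the one tabulated.

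The cost is one or two sentences per document and one programming rule comparing on-treatment with pre-dose grade. SAP 12 already defines baseline as the last value before first dose, which gives the comparator where a pre-dose grade is recorded. Protocol 10.8 asks for onset date, resolution date and severity but does not mention the date of a grade change, so confirm that the eCRF holds that date or opens a new record. The downside is that TEAE counts may be slightly higher.

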11.7 Post Treatment Follow up

If the reason for the discontinuation was other than disease progression, tumor assessments will continue to be performed after treatment discontinuation in approximately 8-12 week intervals until progression.

Tumor assessments to be conducted at these visits. Assessments of adverse events and concomitant medications may also be conducted if adverse events were not resolved at the time of the End of Treatment visit.

In subjects who have experienced a response and in whom only residual tumor tissue remains, irradiation of the remaining tumor lesions will be permitted as per standard of care.

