6.4. Handling of Dropouts or Missing Data

The primary analysis will be based on the observed available data – no data imputations will be conducted. For the survival analysis, dropouts without confirming events will be treated as censored.

As part of the exploratory analysis, sensitivity analysis using appropriate data imputation models may be conducted. The impact of different imputation models will be assessed and compared to main analysis.

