9.1. Adverse Events

The following adverse event tables will be displayed:

- Overall summary of TEAEs, to include total number of TEAE, frequency of subjects with TEAEs, drug-related TEAEs, SAEs, drug-related SAEs, Grade 3 or higher TEAEs, drug-related Grade 3 or higher TEAE, or death within 30-days within administration of study-drug, and AEs leading to permanent discontinuation of study drug
- Overall summary of exposure-adjusted TEAE incident rates, calculated as number of events per cycle, and corresponding 95% confidence intervals frequency and percentage of TEAEs by SOC and preferred term (PT)
- Frequency and percentage of TEAEs by SOC/PT by maximum CTCAE toxicity grade
- Frequency and percentage of hematology-related TEAEs by SOC and PT
- Frequency and percentage of hematology-related TEAEs by SOC/PT by maximum CTCAE toxicity grade
- Frequency and percentage of chemistry-related TEAEs by SOC and PT
- Frequency and percentage of chemistry-related TEAEs by SOC/PT by maximum CTCAE toxicity grade
- Frequency and percentage of renal-related TEAEs by SOC and PT

- Frequency and percentage of renal-related TEAEs by SOC/PT by maximum CTCAE toxicity grade
- Frequency and percentage of Grade 3 or 4 toxicities with PT of Fatigue
- Frequency and percentage of Grade 3 or 4 toxicities with SOC of Gastrointestinal Disorders
- Median duration in days for all TEAEs by SOC/PT
- Frequency and percentage of study-drug related TEAEs by SOC/PT
- Frequency and percentage of Grade 3 or higher study-drug related TEAEs by SOC/PT
- Frequency and percentage of SAEs by SOC/PT
- Frequency and percentage of study-drug related SAEs by SOC/PT
- Frequency and percentage of TEAEs leading to permanent discontinuation of study drug

Per subject listing of AE information will be provided. Per subject detailed information of SAE, Death on Study, and AEs that lead to study discontinuation will also be provided in separate listings.

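### AEs still ongoing are given a stop date at an undefined last contact and pooled with resolved AEs, so the median AE duration can be wrong in either direction

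*SAP*

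**What the plan says.** Duration is a stated safety measure, named beside incidence and severity in SAP section 9 and Protocol section 12.2.2. SAP section 9 then sets the calculation:

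- Events included: "AE durations will be calculated using all TEAEs".
- Unresolved events: "For AEs that are still ongoing at the end of study", the SAP says, "we will use the last contact date as the end of AE stop date for calculating the duration of AEs".
- Summary: "Median, minimum and maximum of AE durations will be reported".

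SAP section 9.1 carries this into a planned table: "Median duration in days for all TEAEs by SOC/PT". Neither section plans a censoring flag, a count of ongoing AEs or a sensitivity analysis for duration.

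Censoring is used elsewhere. SAP section 6.4 says "For the survival analysis, dropouts without confirming events will be treated as censored". SAP section 8.2 censors a maintained response at the last evaluable assessment without progression and analyses DOR and PFS by Kaplan-Meier.

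On AE follow-up, Protocol section 10.9 ends the reporting period at a point "defined as 30 days from the final administration of the trial treatment or immediately before initiation of any other anticancer therapy", whichever is first. Under Protocol section 11.7, later AE assessments "may also be conducted if adverse events were not resolved at the time of the End of Treatment visit". Protocol section 10.12 requires AEs possibly related to study drug to be followed to stabilization or a known outcome. After progression, Protocol section 11.7.1 has contacts about every 12 weeks for survival and subsequent therapy, possibly by phone. It lists no AE status for these contacts.

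**The concern.** An AE that has not resolved has a right-censored duration: we know only that it lasted at least until its status was last checked. The SAP enters it as a completed duration. The resulting median mixes true durations with cut-off ones, and the table does not show how many of each it contains.

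The date is a second problem. AE status and survival status are collected on different schedules, and survival contacts can continue well after AE reporting has closed. If last contact means the last AE assessment, the assigned duration is a lower bound. If it means a later survival call, an AE last recorded as ongoing is extended over a period in which nobody asked about it.

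At stake is how persistent the toxicities appear to be. The current amendment adds up to 20 subjects specifically to characterize safety and tolerability further, so a reader of the report may rely on these medians.

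**Working it through.** The plan states no AE-duration figure, so there is none to reproduce. The share of AEs ongoing, the true durations and the gap between last AE assessment and last contact are not in the documents either. All of these are assumptions below.

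**Step 1. Direction when the AE is present at last contact.** Each assigned duration is then no longer than the true one, so the sample median can only fall or stay the same. It stays the same when every ongoing AE already lies above it. Example: durations 3, 5, 7, 9, 12, 14, 20, 60, 90 and 120 days, the last three ongoing. The median is (12 + 14)/2 = 13 days, whatever the true stop dates of those three.

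**Step 2. Size, with a 30-day minimum of follow-up.** Protocol section 10.9 gives about 30 days of AE reporting after the last dose, so an AE starting on treatment is normally observed for about 30 days or more. Assume exponential durations with true median m, rate λ = ln 2/m, and last AE assessment uniform between 30 and 30 + w days after onset, equal to last contact. For t below 30 days nothing is cut off. Above 30 days the SAP's median t solves

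exp(−λt) × [1 − (t − 30)/w] = 0.5,

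and the share ongoing is exp(−30λ) × [1 − exp(−λw)]/(λw).

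- m = 28: half of the AEs have resolved by day 28, before any can be cut off. The median is 28 days for every w, with 6% to 25% ongoing for w = 300 to 60.
- m = 60, λ = 0.01155:

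| w (days) | Share ongoing | SAP median (days) |
|---|---|---|
| 300 | 20% | 53.1 |
| 150 | 34% | 48.6 |
| 90 | 44% | 44.6 |
| 60 | 51% | 41.5 |

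Check for w = 60: exp(−0.01155 × 41.5) = 0.619 and 1 − 11.5/60 = 0.808; the product is 0.500. Share ongoing: 0.707 × 0.5/0.693 = 0.51.

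**Step 3. Sensitivity to the 30-day minimum.** Death, withdrawal, early new therapy or onset after the last dose can shorten follow-up. With last assessment uniform from day 0 to w, the equation is exp(−λt) × (1 − t/w) = 0.5. A true 28 days then becomes 24.6, 21.7, 18.6 and 15.7 days for w = 300, 150, 90 and 60, with 13.5%, 26%, 40% and 52% ongoing. The size therefore depends heavily on an input that the documents do not give.

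**Step 4. Last contact is a later survival call.** Suppose it falls 84 days (12 weeks) after the last AE assessment and AE status was not updated. In simulations with Weibull durations (shape 0.7, 1.0 and 1.5) and last AE assessment uniform from day 0 up to 60 to 400 days after onset, a true 14 days is reported as 14.3 to 17.4 days and a true 60 days as 65.9 to 101.2 days. With a 28-day gap the 14-day case is already too high (14.3 to 17.4), while the 60-day case is still too low (41.2 to 56.8).

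**Step 5. Does Kaplan-Meier repair it?** In the Step 4 simulations, censoring at the last AE assessment recovers the truth: 13.9 to 14.0 days for a true 14, and 59.8 to 60.4 for a true 60. It is not estimable in two settings with 68% and 72% ongoing. Censoring at a last contact 84 days later does not repair it: in the Step 3 settings a true 28 days gives about 30, 32 and 38 days and then not reached.

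**The case against.** The strongest defence is that the effect may be nil or small. Routine follow-up runs about 30 days past the last dose, so short AEs are seen to their end, and Step 2 shows no bias for a 28-day median. AEs possibly related to study drug are followed to stabilization or outcome, which lowers the share ongoing. The rule is disclosed, it feeds only descriptive tables, and every AE is listed by subject. Kaplan-Meier by preferred term in at most 70 subjects will often be unstable.

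Much of this stands, and it keeps the point minor. It does not remove it. Stabilization is not resolution, so unresolved AEs remain; longer durations are still understated; and nothing shows the reader of the table how many durations were cut off.

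A reader might infer that the reported medians are always too low. The documents do not support that: last contact is undefined, survival contacts outlast AE reporting, and Step 4 shows the error can be upward. Nor do they show which AEs were left unresolved, so naming particular toxicities as understated would be speculation.

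**Conclusion.** The point holds in a conditional form. The SAP treats right-censored AE durations as complete, at an undefined date, so the reported median can be wrong. It is too low or unchanged if the AE was present at last contact, and can be too high if last contact is a survival call without AE assessment.

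The size cannot be derived from the documents. The 42 to 53 days for a true 60, and the absence of effect for a true 28, rest on exponential durations, at least 30 days of follow-up after onset, and last contact equal to the last AE assessment. They are illustrations, not predictions.

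AE incidence, grade tables and ORR are untouched. This is a low-severity point that is worth correcting because the change is small.

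**What to change.** In SAP section 9, replace the stop-date rule as follows:

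- Censor ongoing AEs at the last date on which AE status was assessed, not at last contact, and state a rule for subjects who die with an AE ongoing.
- Report the Kaplan-Meier median and the number of AEs ongoing per SOC and preferred term in the section 9.1 table.
- Keep minimum and maximum over all TEAEs and mark values from ongoing AEs as censored, for example 120+. Restricting the maximum to resolved AEs would hide the longest unresolved ones: in the Step 1 example it would drop from 120 to 20 days.

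The cost is a paragraph of SAP wording and one procedure. The downside is that some preferred-term medians will be unstable or not reached. At a minimum, define last contact for this purpose and print the number ongoing beside each median.

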10.4 Abnormal Laboratory Findings and Other Abnormal Investigational Findings

Abnormal laboratory findings and other abnormal investigational findings (e.g. on an ECG trace) should not be reported as AEs unless they are associated with clinical signs and symptoms, lead to treatment discontinuation or are considered otherwise medically important by the Investigator. If an abnormality fulfills these criteria, the identified medical condition (e.g. anemia, increased ALT) must be reported as the AE rather than the abnormal value itself.

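### The SAP's mapping list for hematologic adverse events has no hemoglobin line, so any event coded as decreased hemoglobin would be left out of the anemia row

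*SAP*

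**What the plan says.** SAP section 9 sets a rule for tabulating hematologic adverse events: "Hematologic abnormalities reported as AEs that were coded to preferred terms in the Investigations SOC will be mapped to appropriate terms". The target is the Blood and Lymphatic System class. The rule is limited to a stated list of categories, and the list has four entries:

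- "Platelet count decreased = Thrombocytopenia"
- "Neutrophil count decreased = Neutropenia"
- "White blood cell count decreased = Leukopenia"
- "Lymphocyte count decreased = Lymphopenia"

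Nothing in the list concerns hemoglobin. The same section includes hemoglobin in the hematology panel and counts a subject once per system organ class and once per preferred term.

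Protocol 12.2.2 treats anemia as one of three named hematologic toxicities: "The incidence of grade 3 and 4 hematological toxicities (including neutropenia, thrombocytopenia, and anemia) will be provided by treatment cycle".

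Protocol 10.4 bears on how often a hemoglobin term could arise. When a laboratory abnormality qualifies as an adverse event, "the identified medical condition (e.g. anemia, increased ALT) must be reported as the AE rather than the abnormal value itself".

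**The concern.** A programmer who follows the list will move four kinds of cell-count term and leave any hemoglobin term where it was coded. Two of the three toxicities named in Protocol 12.2.2 have a merging rule and the third has none. Neither SAP section 9 nor the list of changes in SAP section 14 gives a reason.

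The tables exposed are those in SAP 9.1 built on system organ class and preferred term: all TEAEs, maximum grade, hematology-related, drug-related, Grade 3 or higher drug-related, serious events and median duration. For milder and drug-related anemia, no other summary fills the gap. The laboratory tables in SAP 9.2 start at Grade 3, SAP section 14 drops laboratory change and shift from baseline, and the remaining laboratory results appear only in listings.

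Safety is Secondary Objective 2, and the 20-subject extension was added to characterize safety and tolerability. Anemia is also common here: Protocol 9.4 reports Grade 3 or higher anemia in 39% of stage 1 and 2 subjects.

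**Working it through.** **Step 1. Compare the list with the panel and the named toxicities.**

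| Item | In SAP 9 hematology panel | Named in Protocol 12.2.2 | Has a mapping line in SAP 9 |
|---|---|---|---|
| Platelets / thrombocytopenia | yes | yes | yes |
| Neutrophils / neutropenia | yes | yes | yes |
| Hemoglobin / anemia | yes | yes | **no** |
| White cells / leukopenia | yes | no | yes |
| Lymphocytes / lymphopenia | yes | no | yes |

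**Step 2. Effect on the anemia row.** Let N be the number of subjects treated, a the number with an adverse event coded as anemia, and k the number with a decreased-hemoglobin event and no anemia event.

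- Row without the mapping: a/N
- Row with the mapping: (a + k)/N
- Understatement: k/N

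Subjects with both terms are already in a, so their incidence does not change. Their maximum anemia grade could be too low if the higher grade sits under the hemoglobin term.

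**Step 3. Size per subject.**

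- N = 70 (maximum enrollment): 1/70 = 1.4 percentage points
- N = 18 (stages 1 and 2): 1/18 = 5.6 points
- N = 12 (planned CXCL12+ cohort): 1/12 = 8.3 points. This matters because SAP 7.1 presents subjects by subtype throughout.

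**Step 4. Illustration.** No figure in the plan depends on this rule, so there is none to reproduce. The stage 1 and 2 percentages in Protocol 9.4 fit a denominator of 18: neutropenia 15/18 = 83%, thrombocytopenia 11/18 = 61%, leukopenia 9/18 = 50%, anemia 7/18 = 39%, febrile neutropenia 6/18 = 33%, lymphopenia 3/18 = 17%. Suppose 7 of 18, or an assumed 27 of 70, are recorded under anemia:

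| k (assumed) | N = 18: (7 + k)/18 | N = 70: (27 + k)/70 |
|---|---|---|
| 0 | 38.9% | 38.6% |
| 1 | 44.4% | 40.0% |
| 2 | 50.0% | 41.4% |
| 3 | 55.6% | 42.9% |

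The documents do not give k.

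**Step 5. Where the rule does not reach.** The Grade 3/4 incidence by cycle in Protocol 12.2.2 has its counterpart in SAP 9.2, under laboratory evaluations, and SAP section 9 grades laboratory tests by CTCAE v4.03. If that table is built from hemoglobin values, a preferred-term mapping cannot change it. The SAP does not say outright that laboratory values are its only source.

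**The case against.** The strongest reply is that the gap may be empty. Protocol 10.4 uses anemia as its own example of a condition to be reported in place of the abnormal value, and neither document reports an event coded to a hemoglobin term. The Protocol 9.4 list of Grade 3 or higher events in more than 10% of subjects contains no such term. Since 2/18 = 11.1% exceeds 10%, a complete list would allow at most one of the 18 subjects to carry that term at Grade 3 or higher. Coding follows a Data Coding Plan that is not among the documents and may already settle the matter. The four entries may also reflect the terms actually seen in the data.

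Much of this stands. It makes k small or zero plausible. It does not close the gap, for three reasons. The reporting rule in Protocol 10.4 applies equally to the four cell-count terms, and the SAP still mapped them. The Protocol 9.4 list is introduced as an inclusion, covers only stages 1 and 2, and says nothing about lower grades. The SAP does not state that its list was drawn from the coded data.

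It is also fair to say that the SAP plans no formal comparison between toxicities, and that an unmapped hemoglobin event would still appear in the TEAE tables and listings, where a reader could find it. But that reader could not add the two rows reliably, because some subjects may be in both.

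**Conclusion.** The omission is real and the consequence is conditional. The list lacks a hemoglobin line. If any treated subject has a decreased-hemoglobin event and no anemia event, the anemia row in the SAP 9.1 tables is understated by k/N, or 1.4 percentage points per subject at N = 70. If there is no such subject, incidence is unaffected. This rests on the list being applied as written and on the Data Coding Plan not already merging the terms. It is a minor point with no bearing on the primary endpoint.

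Three stronger readings are tempting and are not supported:

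- A reader might infer that anemia is in fact split and understated. That needs k above zero, which the documents do not show.
- A reader might scale the reported 39% down by an assumed 10 to 30%, giving 7/18 × 0.9 = 35.0% to 7/18 × 0.7 = 27.2%. That treats 39% as the fully merged rate, whereas it is what was already reported as anemia. Merging could only leave it unchanged or raise it, and the 10 to 30% share has no source in the documents.
- A reader might infer that the Grade 3/4 incidence promised in Protocol 12.2.2 will be wrong. If it is built from laboratory values, it will not be.

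**What to change.** Add one entry to the SAP section 9 list, *Hemoglobin decreased = Anemia*, and state that the existing once-per-subject and maximum-grade counting is applied after mapping. Related terms such as red cell count or hematocrit are not needed on the documents' evidence, since neither test is in the hematology panel. Alternatively, check the coded terms before database lock and record in the SAP that no decreased-hemoglobin term occurs.

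It would also help to say whether the Grade 3/4 hematology incidence by cycle comes from laboratory values alone.

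The cost is one line in the SAP and one in the coding or derivation step. No new data are needed, and if no such terms exist the output does not change.
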